### **Research Population & Recruitment Methods:**

The sampling frame for the proposed research is community-dwelling adult women and men with HF and their spouse care partner.

Formal inclusion and exclusion criteria for patient participants are:

Inclusion criteria:

Willing and able to provide written informed consent

Age greater than or equal to 18 years

Diagnosis of HF

Current HF symptoms (i.e. NYHA Class II-III; AHA/ACC Stage C HF)

Reachable by telephone/email/texting

Access to device with camera (e.g., computer, tablet) to participate in Zoom sessions or phone

Have a co-residing spouse/unmarried partner willing to participate

Exclusion criteria:

Major and uncorrected hearing impairment

Significant cognitive impairment

Heart transplantation/mechanical circulatory support prior to enrollment

Concomitant terminal illness that would impede participation in a longitudinal study

Active psychosis or severe substance abuse that would impair the ability to complete the study

Inability to complete the requirements of the study, including enrolment in an additional intervention trial

Formal inclusion criteria for spouse care partner participants are:

Age greater than or equal to 18 years

Co-residing with the patient at the time of recruitment

Have lived with the patient for a minimum of one year similar to other couple studies

Be willing and able to provide written informed consent

*Inclusion Criteria Justification:* An approximately equal number of women and men with heart failure will be enrolled. No potential participant will be excluded based on gender, race or ethnicity.

With 72 couples (144 participants total), and allowing for a 17% missing data rate, i.e. 60 dyads), we have 80% power to detect a 6.6 point difference in dyadic PROMIS global health scores between intervention and control groups (score mean=50, SD=10), which is greater than a minimally clinically important difference (estimate of  $\frac{1}{2}$  SD (5) due to no additional estimates available). These preliminary data are required to determine the sample size needed for a larger trial.

HF patients are generally older, though it can occur at any age. Those younger than 18 will not be approached for enrollment as the underlying heart failure pathology (e.g. congenital heart defects) is dissimilar to those with coronary artery disease, hypertensive heart failure and other forms of cardiomyopathy and our focus on couples renders the study not relevant to children. Based on epidemiologic data, we anticipate an age range of 18 to 90 with an average of approximately 60-70 years. Our previous HF patient samples have had means of approximately 57 years of age. We anticipate that spouses/unmarried partners will have a similar age distribution. HF occurs in both genders and in persons of all races and ethnicities. No potential participant will be excluded based on gender, race, ethnicity, or sexuality. As an equal number of men and women comprise the HF patient population, approximately equal numbers of men and women will be enrolled in the proposed study (along with their spouse/partner). Specifically, we plan to stratify our randomization by patient gender to ensure equal representation of patient gender across our intervention and attention-control conditions. As with our previous HF research, if enrollment in the total sample becomes imbalanced, every effort will be made to increase the enrollment of the underrepresented gender.

Robust enrollment and retention of persons from minority populations is absolutely desired in the proposed study to achieve our goal of a representative sample of patients with HF (and their care partners). Planned enrollment is based on the distribution of race in Massachusetts where the sample will be drawn. Most recent data shows 80.8% of people in Massachusetts are Caucasian (71.4% Caucasian non-Hispanic or Latino), 8.9% are African American, 7.1% are Asian, 0.5% are American Indian/Alaska Native, 0.1% are Native Hawaiian/Other Pacific Islander, 2.5% report two or more races and 12.3% are Hispanic or Latino.

<https://www.census.gov/quickfacts/MA> We, therefore, believe we can attain a diverse and representative sample in recruiting at least 7 African American dyads (10%), 7 Asian dyads (10%), and 1 Native American Indian and Alaska Native dyads (0.1%). We also hope to recruit approximately 10 dyads (13%) who identify as Hispanic or Latino. We are firmly committed to a representative sample. We will actively target and oversample, where possible, potential minority participants. If our strategies to recruit persons from minority populations are not effective, we will consult with colleagues who specialize in HF research among specific minority groups for alternative strategies. We believe we can attain a sample where 25% of participants identify with a racial minority.

The targeted sample is 72 community-dwelling couples with heart failure (72 HF patients & 72 spouse care partners) with equal patient gender representation (36 couples per condition) to maximize ability to generalize. We will recruit approximately 6 dyads per month during 12 active months of recruitment for a total of 72 couples through the community and social media and referrals from Tufts Medical Center, Atrius Health and other cardiology professionals within our network.

We will use standard recruitment procedures that have been successful in our prior couple studies.

Recruitment flyers will be shared in the community and through social media to advertise the study. Flyers will

provide interested heart failure patients with information about the study and contact information for the Boston College research team. Those dyads who are interested in the study and contact the research team will be screened by study staff not directly involved with patient care. Study staff will speak with both members of the interested HF dyad and determine eligibility. If both members of the HF dyad are interested and eligible, the project coordinator will ask participants to carefully read and provide written informed consent using an online consent/HIPAA authorization form via our Research Electronic Data Capture (REDCap) platform. (In rare circumstances where participants cannot or do not want to complete this process electronically we will mail a consent form and stamped, addressed return envelope). Regardless of mode, we will describe the study in detail, make sure participants have all of their questions about the study addressed and obtain written informed consent from all participants. Heart failure patients are often older in age, so as in our past studies, the option for reading the consent form detailing the requirements of participation will be offered to both patients and their care partners. In fact, reading aloud the entire consent form to potential participants has become the standard default in our current research. A copy of the consent form will be provided/sent to each participant (both members of the heart failure dyad). Participants can ask questions regarding the study on an ongoing basis. Waiver of elements of informed consent or HIPAA authorization will not be sought. We will not use parental consent, assent procedures, or any other form of proxy consent in this study.

**Tools that will be used to recruit** Recruitment flyers distributed in the community and through social media.

**Research Incentives and Payments:** Dyads will also be compensated with a \$100 gift card for their participation.

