### **C. Materials, Methods and Analysis**

The proposed study is a two-group randomized controlled trial with separate assessments of patients and spouse care partners at 0, two months and five months. A community-based sample of patient-spouse care partner dyads will be recruited and randomly assigned by block (patient gender) to either the *Taking Care of Us* intervention or to an educational attention-control. All sessions will be delivered via Zoom (or phone) - there will be no in-person contact with participants throughout the study. *The term spouse refers to spouse or*

*unmarried partner.* All participants will be assessed three times baseline, two months and five months. We believe 7 biweekly sessions over two months, with the first follow-up interview taking place immediately at two months is realistic and appropriate. Our second follow-up will take place at five months to explore sustained effects. The attention-control group will receive three educational sessions over two months (at approximately 0-, 4- and 8 weeks). The sampling frame for the proposed research is community-dwelling adults with NYHA class II-III HF and their spouse/partner. The target sample is 72 couples with HF (36 couples per arm) with equal gender representation.

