*individual health (i.e., lower care-related strain and better HF-specific QOL) compared with HF dyads in the control group.* Aim 2: To determine the efficacy of the *Taking Care of Us* intervention on dyadic appraisal & dyadic management. *Hypothesis: HF dyads in the Taking Care of Us group will have more similar appraisal of patient symptoms (i.e., dyspnea, pain, fatigue), greater collaboration in HF management behaviors and shared activities, and greater communication and dyadic confidence compared with HF dyads in the control group.* For Aims 1 & 2 we will have the following procedures. First, we will run a series of longitudinal APIM (matched pairs) models to simultaneously examine patient and care partner trajectories in health, depressive symptoms, anxiety, perceived dyadic health and healthcare utilization (Aim 1), engagement in heart failure behaviors, shared activities, communication and confidence (Aim 2) over time (controlling for interdependent data). Each HLM Level 1 model has four coefficients representing intercepts (baseline assessments) and slopes (rates of change) for patients and care partners that become outcome variables in an unconditional Level 2 model. Conditional Level 2 models will examine the effect of GROUP on patient and care partner dyadic health and dyadic management variables (controlling for covariates). A significant coefficient for GROUP on the slope parameter and a significantly better fitting model (as evidenced by the deviance statistic) will indicate the rate of change across time is statistically dependent on treatment condition. Second, to examine dyadic symptom appraisal, a longitudinal incongruence model will be used to directly examine patient-care partner dyadic appraisal over time where the slope represents the pattern of change in incongruence (gap in appraisal between the two members of the dyad). Three separate models will be estimated for each outcome (patient dyspnea, pain, & fatigue). We will know how large the gap is, the type of gap (e.g., care partner rating lower than patient), how the gap changes over time (e.g., increases, decreases, remains stable), and how much variability there is around the average pattern of change. The effect of TCU on dyadic appraisal will be tested directly by examining the role of GROUP. Third, for individual level variables (i.e., care strain and HF-QOL) individual MLM will be used to examine the role of GROUP.

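### With 60 dyads, SD 10 and a conventional two-sided 5% test, power for 6.6 points is about 71%, not the stated 80%; 80% needs an assumption the protocol does not state

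*Combined protocol and SAP*

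**What the plan says.** The only power statement for the primary outcome is in Research Population & Recruitment Methods, in the paragraph justifying the inclusion criteria. It starts from the 72 enrolled couples, reduces that number and claims power on the result: "allowing for a 17% missing data rate, i.e. 60 dyads), we have 80% power to detect a 6.6 point difference". The SD is attached to the dyadic score, and the difference is then compared with the important difference: "dyadic PROMIS global health scores between intervention and control groups (score mean=50, SD=10), which is greater than a minimally clinically important difference". The important difference is put at half an SD, or 5 points.

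Section C (Materials, Methods and Analysis) gives the allocation: "The target sample is 72 couples with HF (36 couples per arm) with equal gender representation". The analysis text for Aims 1 and 2, later in section C, sets the criterion for an effect: "A significant coefficient for GROUP on the slope parameter and a significantly better fitting model". It names no significance level. The documents give no alpha, no sidedness, no test for the power calculation, no within-dyad correlation and no correlation between assessments.

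**The concern.** The sentence contains enough to be checked against the usual default, a two-sided 5% comparison of two groups, and on that default it does not reproduce. If the 80% is wrong, a null result will be read against more power than the study had. That matters even in a pilot: efficacy is the primary aim, success is defined by a significant coefficient, and the same paragraph says the data will inform the sample size of a larger trial. Readers are also not told how much power the study has for the 5-point difference that the protocol itself calls important.

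**Working it through.** **Inputs from the protocol.** 72 dyads enrolled, 36 per arm; 17% missing; difference 6.6; SD 10; important difference 5. The count is right: 72 × 0.83 = 59.8, so 60 dyads.

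**Inputs assumed.** Alpha 0.05, two-sided; equal loss, so 30 dyads per arm; SD 10 applies to the dyad score, as the sentence reads.

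**Formulae.** Normal approximation: detectable difference = (z_alpha + z_power) × SD × √(2/n), and power = Φ(difference / (SD × √(2/n)) − z_alpha). The t-test values use the noncentral t distribution with 2n − 2 degrees of freedom.

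**Reproducing the plan's figure.** It appears with all 72 dyads: (1.960 + 0.842) × 10 × √(2/36) = 6.603. The t-test value there is 6.70, with 78.9% power for 6.6.

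**On the stated 60 dyads, two-sided 5%:**

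| Quantity (30 per arm) | t-test | Normal |
|---|---|---|
| Power for 6.6 points | 71.0% | 72.4% |
| Difference with 80% power | 7.36 | 7.23 |
| Power for 5 points | 47.8% | 49.1% |

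The shortfall is 80 − 71.0 = 9.0 points (t-test) or 80 − 72.4 = 7.6 points (normal), too large for rounding.

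**Unstated inputs that would bring power for 6.6 to 80% (30 per arm, t-test unless noted):**

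- *One-sided 5%.* Power for 6.6 is 81.1% (normal 81.9%). The 80%-power difference is 6.50 (normal 6.42), close to 6.6 but not equal to it. Power for 5 points is 60.6%.
- *SD 10 per person, outcome the mean of both partners.* The dyad SD is 10 × √((1 + r)/2). Power is 85.2%, 82.7%, 80.2% and 77.8% at within-dyad correlation r = 0.4, 0.5, 0.6 and 0.7. It reaches 80% when r is 0.61 or lower (normal 0.66).
- *Baseline adjustment.* The SD becomes 10 × √(1 − b²). Power is 75.0% at b = 0.3 and 82.7% at b = 0.5. It reaches 80% when b is 0.44 or higher (normal 0.41).

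**The planned slope test, as an illustration.** Assume one dyad-level score, equal correlation r between the waves at 0, 2 and 5 months, no extra random-slope variance, and a linear effect reaching 6.6 at month 5. The times have mean 7/3 and sum of squared deviations 12.667. The SD of the five-month change implied by a dyad's fitted slope is 5 × 10 × √((1 − r)/12.667):

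| Wave correlation r | SD | Power for 6.6 |
|---|---|---|
| 0.3 | 11.75 | 57% |
| 0.5 | 9.93 | 72% |
| 0.6 | 8.89 | 81% |

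**Power for 5 points if 6.6 is accepted as the 80%-power difference (normal).** Two-sided: Φ(2.802 × 5/6.6 − 1.960) = 56%. One-sided: Φ(2.486 × 5/6.6 − 1.645) = 59%.

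**The case against.** The strongest reply is that this shows undisclosed inputs, not a wrong number. Both partners complete the PROMIS form and the sentence counts 144 participants, so SD 10 could be the individual SD; 60 dyads then give at least 80% power at any within-dyad correlation up to 0.61. The hypotheses are directional, and a one-sided test gives 81%. The trial will fit a three-wave multilevel model with covariates and full maximum likelihood, not an unadjusted t-test on complete dyads. The slope illustration is also simplified: if SD 10 is per person and a within-dyad correlation of 0.5 carries over to the slopes, its 72% at wave correlation 0.5 becomes 83%.

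Much of this stands as a limit on the claim. The 80% is not impossible, and a match with the 72-dyad result does not prove how 6.6 was obtained. But none of these inputs is written down. The sentence attaches SD 10 to the dyadic score, a directional hypothesis does not declare a one-sided test, and the power is tied to 60 dyads whatever partial data the model may recover. The slope model cannot settle the matter, because its power falls on either side of 80% depending on a correlation that is not given.

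It is also fair that any difference below the 80%-power difference has less than 80% power, so calling 6.6 greater than 5 already implies the shortfall. Asking for the figure is the more optional part, and the main point does not depend on it. Pilot status limits how serious this is; it does not make the sentence correct.

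**Conclusion.** The concern holds. With 30 dyads per arm, dyad-level SD 10 and a two-sided 5% test, power for 6.6 points is 71% (t-test) or 72% (normal). The stated 80% is therefore about 8 to 9 percentage points too high, and the 80%-power difference is 7.4 or 7.2 points instead of 6.6. This rests on the assumed alpha and sidedness, equal loss in the two arms, and SD 10 read at the level the sentence gives. Other inputs could support the figure, but the protocol states none of them, so the claim cannot be verified as printed. That the attrition allowance was left out of the calculation is plausible but unconfirmed. The point should be fixed; it does not undermine the design.

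**What to change.** State alpha, sidedness, the test, the level at which SD 10 applies and any correlation used, and give all figures on that one basis. If the conventional reading was intended, the text could run: with 60 evaluable dyads (30 per arm), dyad-level SD 10 and a two-sided 5% t-test, the study has 80% power for 7.4 points, 71% for 6.6 points and 48% for the 5-point important difference. Because this describes a simple two-group comparison, it should be labelled as such and not presented as the power of the slope model.

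If a one-sided test, an individual-level SD with a within-dyad correlation, baseline adjustment or the slope model was intended, state that input with its value and recompute; 6.6 may then stand. In either case, it would help to replace the bare comparison with the important difference by a plain statement that power for 5 points is below 80%, with the figure.

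The cost is one or two sentences and no extra participants. Either the stated figure becomes less favourable, or an assumption has to be written down and defended.

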**Informed Consent Procedure:**

All team members will attend virtual training hosted by the study MPIs. The training will include didactic presentations, roleplaying, feedback and problem solving about performance as well as study procedures and potential issues that may arise during sessions. The program will include information specific to HF and the components of the intervention/education programs as well as training for the RAs. Ongoing training will include review of completed forms to provide feedback on standardized protocol. To ensure independence of observations, interviewer, interventionist and control group educator training will be conducted separately. MPIs will closely monitor the interventionist and control group educator throughout the study to ensure fidelity of implementation by holding bi-weekly meetings. Treatment fidelity will be maximized by developing a standardized intervention manual in the first phase of the study.

The project coordinator and study staff will screen and obtain verbal consent and then direct eligible and interested dyads to complete written informed consent using an online consent/HIPAA authorization form via our Research Electronic Data Capture (REDCap) platform. All study staff will undergo training by the MPIs of the study as well as completing all necessary human subject education training.

After the consent form has been read to the participants we will ask them to summarize their understanding of the study and their participation. Participants will be strongly encouraged to ask questions about procedures and questions at all stages of the process.

Study staff will speak with both members of the interested HF dyad and determine eligibility. If both members of the HF dyad are interested and eligible, they will be asked to provide verbal consent to participate in the study. Once verbal consent has taken place, the project coordinator will first ask participants to carefully read and provide written informed consent using an online consent/HIPAA authorization form via our Research Electronic Data Capture (REDCap) platform.

Regardless of mode, we will describe the study in detail, make sure participants have all of their questions about the study addressed and obtain written informed consent from all participants. Heart failure patients are often older in age, so as in our past studies, the option for reading the consent form detailing the requirements of participation will be offered to both patients and their care partners. In fact, reading aloud the entire consent form to potential participants has become the standard default in our current research. A copy of the consent form will be provided/sent to each participant (both members of the heart failure dyad). Participants can ask

questions regarding the study on an ongoing basis. Waiver of elements of informed consent or HIPAA authorization will not be sought. We will not use parental consent, assent procedures, or any other form of proxy consent in this study.

**Confidentiality:**

Data will be collected via REDCap and stored electronically as de-identified in encrypted, password protected files on the BC server. A separate and protected computer file that contains identifiable data that is necessary to contact participants for follow-up (medical record number, phone numbers, e-mail addresses, and U.S. mailing addresses) will also be kept in an encrypted, password-protected file on the BC server accessible to only the study MPIs and project coordinator. This file will be the only file that can link participant identifying information to the study unique codes.

All participating couples will be assigned a code number and all identifying information will be removed from all data sources (hard copies and electronic copies) so that only code numbers will be used. Codes will not contain any part of the 18 HIPAA identifiers (initials, DOB, MRN). Based on guidance from the Boston College IRB, we will keep one separate and protected computer file that contains identifiable data that is necessary to contact participants for follow-up (medical record number, phone numbers, e-mail addresses, and U.S. mailing addresses). This file will be the only file that can link participant identifying information to the study unique codes. All other data will be de-identified and labeled with unique study codes. All study meetings where protected information will be discussed will be closed and study meeting notes will be completed without reference to identifiable participant information. Although there are options for encryption of email, this team has decided to avoid emailing any identifiable patient information over email due to concerns over breaches of confidentiality. Procedures for maintaining confidentiality will be reviewed at all study meetings to assure compliance.

All participating couples will be assigned a code number and all identifying information will be removed from all data sources (hard copies and electronic copies) so that only code numbers will be used. These unique study codes will not be based on any individual identifying data (e.g., age, DOB). As part of the study protocol, no one except the MPIs and project coordinator will have access to an electronic master list containing names and numbers and other protected health information. This electronic file will be maintained for effective participant tracking and follow-up. The file will be encrypted and password protected and located in a secure, password-protected network folder on the BC server. Consent forms will be similarly stored electronically.

**Statement of potential research risks to subjects** Physical and psychological risks associated with this study are considered no more than minimal. There are three potential risks to participants in the proposed study. First, participants may experience distress or become emotionally upset during the sessions or completion of the questionnaires due to the personal and sometimes sensitive nature of some of the questions/topics. Second, participants, particularly patients may experience fatigue completing questionnaires or sessions. Fatigue has not been a factor in our previous HF research that has included a larger number of measures and, in some cases, blood draws and physical function testing, but if fatigue becomes an issue in either interviews or intervention/control sessions, we will divide sessions up, take breaks and allow participants to delay or discontinue until they are ready to resume. We have, purposely, selected brief measures and contained the number of measures to minimize response burden and fatigue. Third, there is a risk that confidentiality about the patient's heart failure may be compromised by participating in the study. Such a breach of confidentiality has never happened in previous research by this team. We estimate the risk to be minimal in the proposed study and safeguards to protect participants are outlined below. There are no financial or legal risks foreseen related to participating in this study. Participation in the proposed study is completely voluntary and separate from medical care.

Participants will be informed verbally and in writing that they may withdraw from the study at any time.

All risks associated with this study are considered no more than minimal.

